#### **Data Handling, Storage and Protection:**

All research procedures will be conducted in private rooms or in a quiet corner of the waiting area, if preferred by families. The option of completing surveys and consent forms in the waiting room is offered because participating families have preferred to use their time in the waiting room in this manner, based on our prior work.

No serious risks are envisioned for subjects. A potential risk is the possibility of a subject's loss of confidentiality. Subjects are identified in research records indirectly. Information identifying subjects is linked to data record but stored separately. The research protocol is designed to minimize the risk of breach of confidentiality. Collection of identifiable or sensitive information is limited to that absolutely necessary for the research. All potentially identifiable electronic data will be stored (A) directly onto secure data servers hosted by Qualtrics (the UW-licensed web survey engine used to generate and administer the online version of our surveys), accessible only through UW NetID login by PI-designated members of our research team, (B) in password protected documents on data servers and workstations located behind UWSMPH or UWMF HIPAA-compliant firewalls, with access limited to research staff at the PI's instruction, and (C) on encrypted, password-protected external hard drives under double lock and key with access limited to research staff at the PI's instruction. All non-electronic data (some surveys, consent/permission forms) are stored under double lock-and-key such as in a locked drawer within a locked secure room.

In order to collaborate with individuals outside of the University of Wisconsin-Madison to conduct fidelity assessments for intervention group sessions, we will use the Department of Pediatrics Computer Services (Peds IT) Citrix remote access service. Citrix allows users with Pediatrics Active Directory accounts to access network file shares, applications, and a full Windows desktop environment. Authorized clients can securely authenticate with their centrally-managed Active Directory account and use the service from any network-accessible location, from any device that will run a supported Citrix client (Mac OSx, Windows, iOS and others). If the endpoint is not managed by Pediatrics IT, the client will not be allowed to move files between the Citrix network shares and the endpoint, ensuring that files are kept on our secure HIPAA-covered network. Project leaders will notify Pediatrics IT when accounts need to be created and when they are to be disabled. Usernames and temporary passwords are provisions by Pediatrics IT and communicated with the end user, who is prompted to create a new password on first login.

The only data stored on portable devices is data from audio recordings of the group intervention sessions. Additional safeguards are applied to protect these data from risk of breach of confidentiality. Group facilitators will audio record the sessions. The audio recording devices use a digital hard drive (no tapes) and will be stored in a locked cabinet in a locked room after each session. Although our pilot work suggests that these recordings do not typically contain identifiable information, research staff will review the audio recordings to make sure that material recorded is de-identified and then promptly transfer the recordings to the Pediatrics IT Citrix system. Research staff will then erase audio recordings on the devices. At the conclusion of the study, audio recordings will be destroyed by deleting the audio files from the Citrix system.

All research members will be trained regarding human subjects research using the standard, web-based CITI training modules and will possess appropriate HIPAA and human subjects protection certifications. The PI or the research coordinator is available either by pager or cell phone at all times for unanticipated problems or complications.

**Data and Record Keeping:**

The PI will oversee all study procedures, with the research specialists also overseeing the collection and storage of the data. As described previously, all potentially identifiable electronic data will be stored (A) directly onto secure data servers hosted by Qualtrics (the UW-licensed web survey engine used to generate and administer the online version of our surveys), accessible only through UW NetID login by PI-designated members of our research team, (B) in password protected documents on data servers and workstations located behind UWSMPH or UWMF HIPAA-compliant firewalls, with access limited to research staff at the PI's instruction, and (C) on encrypted, password-protected external hard drives under double lock and key with access limited to research staff at the PI's instruction. All non-electronic data (some surveys, consent/permission forms) are stored under double lock-and-key such as in a locked drawer within a locked secure room.

When completed, any such paper forms will be taken to the research office by research assistants immediately after each clinic session. The research assistant will check all forms for accuracy and completeness. Data from these forms will be entered by research assistants into the secure, Qualtrics application described previously. Range checks and consistency checks will be programmed to occur at data entry. Final data will reside in a Stata database with identifying information removed.

Data will be maintained by the PI as long as it proves to be useful for its stated purposes, and a minimum of 7 years from completion. At the appointed time for data destruction, identifiable data files will be deleted from the server and hard drives. Identifiable non-electronic data will be destroyed using the Department of Pediatrics-approved confidential document destruction service.

### **Monitoring and Addressing Potential Problems:**

As described earlier, no serious risks are envisioned for subjects. A potential risk is the possibility of a subject's loss of confidentiality. As described above, the research protocol is designed to minimize the risk of breach of confidentiality. Should any such breach occur, study staff would notify the PI immediately. However, emotional distress can sometimes emerge over time. The research staff will notify the PI within 48 hours of any emotional distress experienced by a study subject and can also provide positive support and encouragement throughout the study to address any such issues. Of course, study participants experiencing emotional distress can discontinue study participation at any point of their choosing. Further, we have the ability to monitor quality of life for control and intervention subjects. Based on prior work with the study's quality of life instruments, a subject experiencing a 1 standard deviation decline in quality of life from baseline at any point in the study would prompt offering supportive care consultation within 48 hours with the clinic social worker or psychologist. Also, based on prior pilot work, we do not anticipate enrollment of subjects with significant substance abuse or mental health issues.

All research members will be trained regarding human subjects research using the standard, web-based CITI training modules and will possess appropriate HIPAA and human subjects protection certifications. The PI or the research coordinator is available either by pager or cell phone at all times for unanticipated problems or complications.

### **Collaborating sites:**

The collaborating sites are Children's Hospital of Wisconsin (Milwaukee, WI) and Nemours Children's Clinic (Jacksonville, FL). The CHW site, under the direction of [name], will recruit and manage subjects for the trial. The Nemours site, under the direction of [name], will provide consultation on study design as well as fidelity assurance for the intervention sessions.

Prior to trial recruitment, all UW and CHW investigators and research coordinators will be trained using standard protocols for all activities. Also, the investigators and research coordinators at UW and CHW will be in weekly email contact to discuss study status and address any regulatory or clinical issues that require attention. There will be

a weekly conference call between these two groups to monitor the study recruitment plan, informed consent process, study protocol compliance, data collection, and data security procedures.

Approximately once a month [name] (PI) will have a conference call with the co-investigator at CHW and [name], co-investigator at Nemour's Children's Clinic whose role is that of a consultant on study design and on intervention fidelity. They will discuss study progress and group session implementation. Results of intervention fidelity will be shared and issues addressed as identified.

All external key personnel will be required to have appropriate certifications. Documentation of course completion will be stored the in UW study office.

If personnel at other sites believe that IRB protocol changes are needed, they will be instructed to communicate with the coordinating center regarding the desired change. The PI will make a determination as to the appropriateness of the proposed change. Any needed protocol amendment will be written by the PI and submitted to the IRB at the coordinating center. Any amended protocols approved by the IRB of record will be communicated to sites via above communication methods. In addition, to ensure each site's compliance to the protocol, a current hard copy or electronic copy of the protocol will be shared with all personnel. Each site's research coordinator will immediately replace previous protocol versions with any amended protocol approved by the IRB of record and communicate this to all investigators and research staff.

Statistical Analysis Plan

Official Title: Family-Centered Tailoring of Pediatric Diabetes Self-Management Resources

NCT Identifier: NCT02024750

Date: 11/22/2017

Data Source

Children aged 8-16 years were recruited from 2 large multidisciplinary diabetes clinics serving both urban and rural populations. We collected A1c data at routine diabetes clinic visits at 9 time points (quarterly during the intervention and for a year after the intervention). Quality of life (QOL) data were collected from parents and children at 5 time points: at baseline, at 3 months after the first intervention session, and at 3, 6, and 9 months after the intervention ended. Fear of Hypoglycemia data were collected from parents at 4 time points: at baseline, at 3 months after the first intervention session, and at 3 and 9 months after the intervention ended.

Analysis Objectives

Applying an intention to treat approach, the primary hypothesis was that outcome trajectories differ between the intervention and usual care arms.

Outcomes

Primary outcomes were trends in A1c for the child, as well as child and parent quality of life. Trend in fear of hypoglycemia was a secondary outcome.

Handling of Missing Values and Other Data Conventions

Rates of missingness were low. Mixed effects regression models were fit via maximum likelihood and were hence robust to non-informative missingness. The influence of informative missing data was evaluated via pattern mixture models. Our evaluations indicated that missing data have no substantial impact on the results of our analyses, so we report results without imputing or modeling missing data.

Statistical Procedures

The primary analytic technique was mixed effects models with repeated measures to capture time trends in intervention and usual care groups via linear terms. Intervention effect was tested via interaction terms between treatment group and time trend, as initially proposed. Trajectories were fit for child's A1c and for QOL for child and parents, as well as fear of hypoglycemia. Preliminary analyses indicated that trajectories differed

between the period during the intervention and post-intervention, so the models allowed the slope of the trajectories before and after the intervention to differ. Outcomes were modeled as continuous, with normally distributed residuals, and within-individual random intercepts and slopes to capture within-individual correlation. Models assuming equal variance of these components in both groups were compared with those allowing unequal variances via likelihood ratio tests. Fixed effects were included in the models to represent block randomization factors (clinic site and age group), and their interactions with time trend were tested.

Measures to Adjust for Multiplicity, Confounders, Heterogeneity, etc.

Two additional variables (i.e., whether the child used an insulin pump and whether the participating parent was the child's mother) were included in the model to correct for imbalance between usual care and intervention arms at baseline. We estimated the average treatment effect for all participants as well as by site and age sub-groups in consideration of potential heterogeneity of treatment effects.

Sensitivity Analyses

Additional covariates (e.g., baseline demographics, healthcare utilization, and comorbidities) were evaluated for inclusion in our models to improve precision. Ultimately, these adjustments for precision made no substantive difference in the study findings, so we report our findings without these covariates.

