### **Statistical Considerations:**

A first step in our analyses is the description of our data. Bivariate relationships will be assessed with measures of association such as correlations and regression coefficients for continuous variables and odds ratios for categorical variables. Ordinal and count variables will be collapsed into fewer categories if some levels are sparsely populated. We will undertake a full analysis of the level, reason, and impact of missingness. Several techniques will be applied to assess whether bias from missing data has occurred. These include multiple imputation of missing data elements and pattern mixture models to assess the impact of missed visits.

Analyses will model intervention outcomes with mixed effects models as:

$$g(y_{ft}) = (\beta_0 + a_f) + \beta_1(Intervention)_{ft} + (\beta_2 + b_f)(time)_{ft} + \beta_3(Intervention \times time)_{ft} + \varepsilon_{ft} \quad (\text{Equation 1})$$

where  $g$  is a link function suitable to producing appropriate measures of the intervention's effect for the scale of the outcome  $y$ ,  $t$  = time ( $t=0$ - $X$  time points during or after the intervention),  $f$  = family ( $f=1 \dots 300$  families),  $a_f$  and  $b_f$  are family specific random intercepts and slopes and  $\varepsilon_{ft}$  enters when equation 1 describes a mixed linear model.

The link function  $g$  will be chosen as the identity link for continuous outcomes (e.g., A1c), as the log for count variables, and as the logit for dichotomous variables. Time will be modeled in several ways: as indicator variables, as a pre-post intervention indicator, and as an ordinal indicator. Depending on results of these tests, the interventions' effect will be described for time points combined, as a trend, or at specific time points after initiation. The variance of random slopes and intercepts will be estimated to assess individual variation in time trends.

Covariates will be added to this model to increase precision and/or adjust for any imbalance between intervention arms as needed and will include an indicator for provider and family demographics. We will evaluate adding fixed effects for the site, although it is unlikely that this will significantly improve model fit as there is typically more variation between providers than between sites. All models will be constructed using Stata 12 (StataCorp, College Station, TX).

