The study is powered to evaluate effects on glycemic control and quality of life (QOL), assuming a two-tailed  $\alpha=0.05$ . We conservatively estimated values over time for an individual family would correlate at 0.08. Previous studies suggest moderate effect sizes (0.3-0.50; e.g., 0.-1.0% reductions in A1c or 6-9 point improvements in QOL) for the self-management resources used in this trial. Using a repeated measures approach and considering our outcomes as continuous, samples of 100 families per arm will provide 80% power to detect small to moderate effects (0.2-0.30) on glycemic control and QOL. Power calculations were conducted with PASS 2008. Based on pilot data, we estimate 70% retention of subjects in the trial. Thus, we will recruit 300 families.

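### The SAP splits the mean slope at the end of the intervention but does not say whether the family random slope was split too; if it was not, the standard errors of the A1c arm-by-slope tests may be wrong

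*SAP*

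**What the plan says.** SAP, Statistical Procedures: the trend is linear in time and is tested by arm-by-trend interactions: "Intervention effect was tested via interaction terms between treatment group and time trend, as initially proposed". Preliminary analyses showed different trajectories in the two periods, "so the models allowed the slope of the trajectories before and after the intervention to differ". The random part is given as "within-individual random intercepts and slopes to capture within-individual correlation". One check on the variance structure is described: "Models assuming equal variance of these components in both groups were compared with those allowing unequal variances via likelihood ratio tests".

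Protocol, Statistical Considerations: in Equation 1 the terms a_f and b_f "are family specific random intercepts and slopes", with one b_f multiplying one time term. The coding of time is left open: "Time will be modeled in several ways: as indicator variables, as a pre-post intervention indicator, and as an ordinal indicator".

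Neither document states whether the random slope was split along with the mean slope. Neither mentions a family-clustered (sandwich) variance or correlated residuals. Neither gives a slope SD, a residual SD or a between-period correlation.

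**The concern.** The arm-by-slope interactions are the tests of the SAP's primary hypothesis, so their standard errors carry the inference. With one random slope over 24 months, each family is assumed to keep the same deviation from its arm's mean slope during and after the intervention. If families in fact change course at the end of the intervention by differing amounts, the model has no term for that variation. It goes partly into the independent residual and is misallocated in the standard errors of the period slopes. Serial correlation in quarterly A1c has a similar effect. Comparing variance components between arms cannot reveal either problem, because both can be present equally in the two arms. At stake are the coverage of the confidence intervals and the 5% error rate of the during-slope test, the post-slope test, their joint test and the slope-change contrast.

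**Working it through.** **The plan's own figure.** The documents give no standard error or variance for a slope. The nearest figure is the protocol's power statement: 80% power, 100 per arm, effects 0.2-0.30, within-family correlation printed as 0.08. The number of repeats is not stated. With five, the survey occasions in the protocol's data-collection table, the detectable effect is 2.802 × √(2/100) × √((1 + 4 × 0.08)/5) = 0.204, which agrees. That calculation compares averages over visits and contains no slope, so it cannot size this issue.

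**Inputs from the documents.** Nine quarterly A1c visits (SAP, Data Source), taken as months 0, 3, ..., 24; knot at month 12; two-sided 5%.

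**Assumed inputs (not in the documents).** Intercept SD 1.2, independent of the slopes; residual SD 0.7 (variance 0.49); slope SDs s₁ (during) and s₂ (post) in A1c points per year, with correlation r; complete, balanced data. The ratios below do not depend on sample size.

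**Method.** Find the single-slope covariance W to which maximum likelihood converges when the true covariance is S, by minimising log|W| + tr(W⁻¹S). Call its slope variance g and its residual variance v. On a balanced schedule the estimates equal least squares, so the per-family variances are simple. The design constants are 1.2952 for either period slope, 4.1143 for the change in slope and 1.0667 for the month-24 change.

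- Period slope: true = s² + 0.49 × 1.2952; model = g + v × 1.2952.
- Slope change: true = s₁² + s₂² − 2r·s₁s₂ + 0.49 × 4.1143; model = v × 4.1143.
- Month-24 change: true = s₁² + s₂² + 2r·s₁s₂ + 0.49 × 1.0667; model = 4g + v × 1.0667.
- R = √(true/model); actual error = 2Φ(−1.96/R).

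**Equal SDs 0.5, r = 0.3** (g = 0.1593, v = 0.5022). Each slope: true 0.25 + 0.635 = 0.885; model 0.159 + 0.650 = 0.810; R = 1.045; error 6.1%. Slope change: 0.35 + 2.016 = 2.366 against 2.066; R = 1.070; error 6.7%.

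**Equal SDs 0.8, r = −0.3** (g = 0.2086, v = 0.5478). Each slope: true 0.64 + 0.635 = 1.275; model 0.209 + 0.710 = 0.918; R = 1.178; error 9.6%. Slope change: 1.664 + 2.016 = 3.680 against 2.254; R = 1.278; error 12.5%. Month-24 change: 0.896 + 0.523 = 1.419 against 0.834 + 0.584 = 1.419; R = 1.00.

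**Unequal SDs, 0.8 during and 0.5 after, r = 0.3** (g = 0.2765, v = 0.5126). The model variance is 0.940 for both slopes. During: true 1.275, R = 1.164, error 9.2%. Post: true 0.885, R = 0.970, error 4.3%, so this standard error is too large.

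| Slope SDs (during/post), r | During | Post | Change | Joint 2-df |
|---|---|---|---|---|
| 0.5/0.5 or 0.8/0.8, r = 1 | 5.0% | 5.0% | 5.0% | 5.0% |
| 0.5/0.5, r = 0.3 | 6.1% | 6.1% | 6.7% | 6.1% |
| 0.8/0.8, r = −0.3 | 9.6% | 9.6% | 12.5% | 10.3% |
| 0.8/0.5, r = 0.3 | 9.2% | 4.3% | 8.1% | 7.2% |
| 0.8/0.4, r = 0.5 | 9.4% | 3.4% | 7.3% | 6.7% |
| 0.3/0.3, r = 0 | 5.7% | 5.7% | 5.9% | 5.6% |

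**Serial correlation instead of changing slopes.** I assumed an exponentially decaying process with variance 0.3 or 0.7 and decay of 3 to 12 months, plus independent noise of variance 0.1 or 0.49. Each slope test then has 7.0-11.6% error.

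**QOL.** The SAP visits fall at about months 0, 6, 15, 18 and 21 (first session at month 3, last at month 12). With the same variance ratios and equal slope SDs, each slope test has 5.2-7.0% error.

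**Check of the remedy.** I used 1,000 simulated null trials at 105 per arm (300 × 0.70 / 2), slope SD 0.8 and r = 0. One random slope gave 7.5% (during) and 9.5% (post); family-clustered robust standard errors gave 4.4% and 5.3%. Under serial correlation with 6-month decay the figures were 9.3% and 11.1%, against 4.0% and 4.6% with robust standard errors. The Monte Carlo standard error is about 0.7 points at 5%.

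**The case against.** The strongest reply is that the defect is not documented. The SAP's plural wording fits a random slope for each period as well as a single one. Equation 1 predates the split and leaves the coding of time open. Because b_f multiplies the same time term as the fixed slope, recoding time into two pieces could naturally have carried b_f into both. The SAP is a short retrospective summary, so its silence on a one-versus-two-slope comparison does not show that none was made.

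Second, a change in mean slope does not imply that families' deviations change. A shift common to all families leaves b_f intact, and then the error is exactly 5.0%.

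Third, every variance used above is assumed. Small slope SDs (0.2-0.3, r from 0 to 0.3) give only 5.2-5.7%, equal SDs of 0.5-0.8 with r = 0.7 give 5.4-5.8%, and unequal SDs can make one period's test conservative. The serial-correlation case could be raised against any random-slope model with independent residuals.

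All of this stands, and it limits the point to a conditional one. It does not remove it: the structure that determines the standard errors of the primary tests is unstated, the only equation on file has the vulnerable form, and no described check or robust variance protects against it.

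**Conclusion.** The point holds conditionally. If A1c was fitted with one random slope and independent residuals, and family slopes differ between periods or A1c is serially correlated, the arm-by-slope standard errors are wrong. Under the assumed SDs with equal slope variability in the two periods, each A1c slope test runs at about 6-10% and the slope-change contrast at about 7-13%. The error disappears when family slope deviations are the same in both periods and is small when slope variance is small. The month-24 change in A1c is unaffected, and QOL is affected less.

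A reader might infer that a single slope was certainly fitted. The documents do not establish this; it is an inference from Equation 1. A reader might also infer that all the standard errors are too small. That does not follow either: with SDs of 0.8 during and 0.5 after, the during test is at 9.2% and the post test at 4.3%. Nor do the documents show that any reported finding is a false positive.

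**What to change.** State in the SAP whether the random slopes are period-specific. Report family-clustered robust standard errors for the arm-by-slope tests of all outcomes. For A1c, with nine visits, fit a random intercept and a random slope for each period with unstructured covariance, if this was not already done. For QOL (five visits, only two of them at or before month 12) and fear of hypoglycemia (four visits), a separate random during-slope is weakly supported, so keep one random slope and rely on the robust standard errors.

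The cost is a refit with a changed random-effects specification and a robust-variance option, plus possible convergence work. Confidence intervals may widen somewhat. No new data are needed. With complete, balanced data the slope estimates themselves do not change; with missed visits they may move slightly.

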**Project Summary:**

The primary goal of this project is to compare the effectiveness of a family-centered approach to diabetes self-management resources (intervention) with the untailored approach of usual care. Diabetes self-management resources will be tailored to families' unique self-management barriers as identified by a 10-minute survey tool called PRISM (Problem Recognition in Illness Self-Management). Based upon the results of PRISM, families will receive self-management resources aligned to address their identified barriers. We will coordinate group-based delivery of the resources with routine diabetes clinic visits. These group-based resources will be delivered in four 75-minute sessions over a year. To assess the effectiveness of the intervention, we will examine glycemic control (A1c), fear of hypoglycemia, and quality of life for the child and parent.

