## **Research Design and Method**

### **Study Population:**

The total number of subjects is 300 families (family being a child with type 1 diabetes and their parent).

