**Study Activities:**

Screening for eligibility takes place at or up to 6 weeks before baseline data collection. Once determined to be eligible and informed consent is obtained, data collection elements and time points for usual care (U) and intervention (I) subjects proceed as in the timeline below.

Data collection for usual care (U) and intervention (I) groups							
Data Element	Baseline (0 months)	Session 1 (3 months)	Session 2 (6 months)	Session 3 (9 months)	Session 4 (12 months)	6 month post (18 months)	12 month post (24 months)
Glycemic control							
A1c	U, I	U, I	U, I	U, I	U, I	U, I	U, I
Fear of hypoglycemia	U, I		U, I		U, I	U, I	U, I
QOL							
Parent	U, I		U, I		U, I	U, I	U, I
Child	U, I		U, I		U, I	U, I	U, I
PRISM	U, I		U, I		U, I	U, I	U, I
Covariates							
Family characteristics	U, I				U, I		U, I
Disease and regimen factors	U, I				U, I		U, I

The first outcome of interest is *glycemic control*, measured by A1c and fear of hypoglycemia. A1c is routinely obtained during clinic visits by point of care A1c. This outcome measure is continuous, but values could also be used to understand whether diabetes control is adequate (A1c values meets American Diabetes Association criteria). Fear of hypoglycemia will be assessed with standard tools for the parent and the child (15 items, survey burden 3 minutes), when age-appropriate. The second main outcome of interest is *QOL*, for both the parent and the child. The child and parent will complete these survey items (survey burden 10 minutes). For the child, we will assess diabetes-specific QOL, measured by the total scale score (33 questions). Although prior work with this instrument suggests children as young as 7 years can complete the survey unassisted, research staff will be available to read the questions to younger children as needed. We will supplement these measures with published items assessing school, work, and play activities (9 questions). For the parent, the adult version of the Peds QL™ Family Impact Module (28 questions) will be used (e.g., impact of diabetes on daily household and work activities, family relationships, and social functioning).

Surveys will also periodically assess change in barrier scores from the PRISM, as well as covariates such as demographics (e.g., child gender or household composition),

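### The intervention is delivered in session groups but the model treats families as independent; if sharing a group makes families' slopes move together, the arm-by-time standard errors are somewhat too small

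*SAP*

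**What the plan says.** **Delivery.** The Protocol's Project Summary says of the intervention: "We will coordinate group-based delivery of the resources with routine diabetes clinic visits" and "These group-based resources will be delivered in four 75-minute sessions over a year". Families are directed to content by their PRISM survey results: "families will receive self-management resources aligned to address their identified barriers". The section on data handling shows that the sessions are led: "Group facilitators will audio record the sessions". The data collection table under Study Activities places the last session at 12 months ("Session 4 (12 months"). Neither document describes sessions or groups for usual care.

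**Model.** In Equation 1 (Protocol, Statistical Considerations) the random terms "are family specific random intercepts and slopes". The SAP (Statistical Procedures) likewise has "within-individual random intercepts and slopes to capture within-individual correlation". It tests the intervention through arm-by-time interactions, with separate slopes during and after the intervention. It compares equal with unequal variance components by arm. It includes clinic site and age group, the block randomization factors, and tests their interactions with time.

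**Not found in either document.** There is no session-group or facilitator term, no cluster-robust variance, no sensitivity analysis for grouping and no allowance for grouping in the power calculation. Group size, ICC, attendance, stability of membership and the way groups were formed are not stated.

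**The concern.** This is a partially nested design: families in one arm share sessions and a facilitator, and families in the other do not. If a group or its facilitator shifts its members' trajectories together, those families' slopes are correlated. A family random slope absorbs the extra variance but assumes zero covariance between families. The mean slope of the intervention arm then looks more precise than it is.

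The existing terms do not repair this. Arm-specific variances change a family's variance, not the covariance between families. Site and age-group terms remove only differences between those strata. The Protocol's provider indicator is optional, is not described as the session group, and does not appear in the SAP model.

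The three primary outcomes (A1c, child QOL and parent QOL) are all judged on arm-by-time tests. With group-caused correlation, intervals for the average effect cover less often than stated, and the test rejects too often when the average effect is zero. Because the sessions end at 12 months, the during-intervention term is the one mainly exposed. The post-intervention term is affected only if the group's influence persists.

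**Working it through.** **The plan's own figure first.** Inputs from the Protocol's power paragraph: 100 families per arm, two-sided 5% level, within-family correlation 0.08, 80% power, effects of 0.2 to 0.30. The number of measures k is not stated there, so it is varied.

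Detectable effect = 2.802 × sqrt(2f/100), with f = (1 + (k − 1) × 0.08)/k.
- k = 2: f = 0.540, effect 0.291
- k = 5: f = 0.264, effect 0.204

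The stated range is reproduced, with all families treated as independent.

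**Standard error under grouping.** Assumptions, because the documents give none: stable groups of m = 4 to 10 families, equal arms, full attendance, and a group-caused ICC of the fitted family slopes of 0 to 0.10.

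DE = 1 + (m − 1) × ICC, in the intervention arm only. Variance ratio r = (1 + DE)/2. SE ratio = sqrt(r). Two-sided error = 2 × (1 − Φ(1.96/sqrt(r))).

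| m | ICC | r | SE ratio | Error |
|---|---|---|---|---|
| any | 0 | 1.000 | 1.000 | 5.0% |
| 8 | 0.01 | 1.035 | 1.017 | 5.4% |
| 8 | 0.05 | 1.175 | 1.084 | 7.1% |
| 10 | 0.10 | 1.450 | 1.204 | 10.4% |

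**ICC as a share of true slope variance.** Fitted slopes contain measurement noise, which a group cannot share. Assume nine quarterly A1c visits (SAP, Data Source), a knot at 12 months, and SDs of 0.7 for each yearly slope and 0.6 for the residual. True slope variance is 0.49 and the noise variance of a fitted slope is 0.466, so the true share is 0.49/(0.49 + 0.466) = 0.51. The ICCs above are multiplied by 0.512:
- m = 8, ICC 0.05: r = 1 + 7 × 0.0256/2 = 1.090, error 6.0%
- m = 10, ICC 0.10: r = 1 + 9 × 0.0512/2 = 1.230, SE ratio 1.109, error 7.7%

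**Partial attendance.** The analysis is by intention to treat, so non-attenders stay in the arm without sharing a group. If 70% attend (an assumption), DE = 1 + 0.7 × (0.7m − 1) × ICC. With the ICC again on fitted slopes:
- m = 8, ICC 0.05: DE = 1.161, error 5.9%
- m = 10, ICC 0.10: DE = 1.420, error 7.5%

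**Which term is affected, and the sorting case.** These are simulations of 40,000 runs with about 100 families per arm, no average effect and the ICC on fitted slopes. The two-slope runs use the A1c visits and SDs above and an intercept SD of 1.2. The sorting runs are on family slopes.

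| Scenario | m = 8, ICC 0.05 | m = 10, ICC 0.10 |
|---|---|---|
| Group effect on during-slope only: during / after term | 6.9% / 5.2% | 9.9% / 5.1% |
| Group effect on both slopes: during / after term | 6.9% / 7.0% | 10.3% / 10.5% |
| Sorting on a baseline trait: family-only test | 4.9% | 5.1% |
| Sorting on a baseline trait: group-variance test | 3.0% | 1.7% |

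**QOL.** The SAP gives five QOL times. With session 1 at 3 months and the last session at 12 months, they fall at about months 0, 6, 15, 18 and 21, so only two precede the knot. With the same SDs carried over as an illustration, the true share of fitted-slope variance is about 31% during and 19% after. A fitted-slope ICC of 0.10 would then need 0.10/0.31 to 0.10/0.19, roughly 33% to 53%, of true slope variance to be caused by the group.

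**Power.** Power = Φ(2.802 × sqrt((n/100)/r) − 1.96), anchored on the stated 80%. "The total number of subjects is 300 families" gives 150 per arm if allocation is equal, or 105 at the Protocol's 70% retention.
- ICC 0: 82% at 105 per arm, 93% at 150
- m = 8, ICC 0.05: 75% and 89%
- m = 10, ICC 0.10: 66% and 81%

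**The case against.** The strongest reply is that no defect is shown. Every input on grouping is assumed. The only routes into groups that the Protocol mentions are the PRISM barrier and coordination with clinic visits, which point to sorting. Sorting of individually randomized families leaves the family-only standard error valid. This stands, and it is why the point is conditional. It does not dispose of correlation that arises after randomization from a shared session or facilitator.

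The second reply also stands: the 10.4% figure needs stable groups, full attendance and about 20% of true A1c slope variance (0.10/0.51) caused by four 75-minute sessions. It is an upper case and not an expected value.

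The third is that the arm-specific variance comparison and the site and age analyses are partial diagnostics. They are, but weak ones, and none estimates covariance between families.

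The fourth is that a session-group model cannot separate sorting from group effects, over-corrects under sorting, and would be weakly identified for QOL with two period-specific slopes. This is right. It argues for a simpler form and for sensitivity status only.

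A reader might infer that the trial's standard errors are known to be wrong, or that the study is underpowered. The documents support neither. No group-caused correlation is documented. The SAP reports low missingness, and at 150 per arm power stays above 80% across the assumed range.

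**Conclusion.** The omission is certain; its consequence is conditional and probably modest. Both models assume that families are independent given their own random effects, although one arm was treated in groups. If sharing a group or facilitator makes slopes move together, the arm-by-time standard errors are too small, chiefly for the during-intervention term.

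For 4 to 10 families per group and a group-caused ICC of 0 to 0.10:
- **ICC as a share of true A1c slope variance** (under the assumed SDs): two-sided error about 5.0% to 7.7%, so 95% intervals cover about 92.3% to 95.0%.
- **ICC as a share of fitted-slope variance, stable groups, full attendance:** error up to 10.4%, falling to about 7.5% with 70% attendance.
- **Sorting only, or sessions that change no family's trajectory:** no inflation.

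The documents do not show which case applies. As written, the analysis gives a reader no group count, group size or ICC with which to judge. This is a low-cost improvement to the analysis and its reporting and does not by itself invalidate the primary result.

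**What to change.** Keep the family-level model as primary. Add one sensitivity analysis for each of A1c, child QOL and parent QOL, with its form written down before fitting. Label it as added, because the SAP is written in the past tense.

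- **Common features:** session-group clustering in the intervention arm only; usual-care and never-attending families as singletons; small-sample degrees of freedom. If membership changed, use the first-session group or a multiple-membership term.
- **A1c:** a group random slope for the during-intervention period, extended to the post-intervention period only if it can be estimated.
- **Child and parent QOL:** a single group-level random slope or a group-clustered small-sample variance, because only two QOL visits precede the 12-month knot.
- **Report:** how groups were formed, their number and size, the ICC with its interval, and whether the conclusion changes. State that the analysis is conservative under pure sorting and that an ICC alone cannot separate sorting from group effects.
- **If membership was not recorded:** state the independence assumption as a limitation, with the range above.
- **Sample size:** disclose only that the 80% power assumes no session-group correlation.

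**Cost.** One further model per primary outcome, and a session-group identifier that neither document says was kept. Intervals may widen. The group variance will be imprecise: about 10 to 26 groups with 105 intervention families (105/10 to 105/4), or 15 to 38 with 150. Under sorting the test over-corrects, rejecting 1.7% to 3.0% instead of 5% in the simulated cases, which is why it should not replace the primary model.
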